### **10.5.2 Binding antibody multiplex assay (BAMA)**

HIV-1–specific total binding IgG antibodies will be assessed using serum samples from study participants taken at the primary immunogenicity timepoints and

baseline. In addition, HIV-1–specific total binding IgA antibodies and binding to IgG subclasses (IgG1, IgG2, IgG3, and IgG4) may also be assessed. Specimens from other timepoints may also be assayed based on the results of the initial assay.

## **10.6 Innate immunity assays**

### **10.6.1 Serum cytokines**

Cytokine multiplex assay and/or enzyme-linked immunosorbent assay (ELISA) will be used to measure soluble cytokines, chemokines, and other immunomodulatory factors in the serum. Analytes may include IFN- $\gamma$ , IL-6, TNF- $\alpha$ , IL-10, IP-10, MCP-1, and/or other analytes may also be included.

## **10.7 Exploratory studies**

Samples may be used for other testing and research related to furthering the understanding of HIV immunology or vaccines. In addition, cryopreserved samples may be used to perform additional assays to support standardization and validation of existing or newly developed methods.

### **10.7.1 Antibody-dependent cellular cytotoxicity (ADCC)**

ADCC activity may be assessed using serum samples from study participants taken at the primary immunogenicity timepoints. Specimens from the baseline and other timepoints may also be analyzed at the discretion of the HVTN Laboratory Program, which may be contingent on the results of the primary immunogenicity timepoints. For the Granzyme B flow-based cytotoxicity assay, participant sera are incubated with effector cells and gp120-coated target. ADCC is quantified as net percent granzyme B activity which is the percent of target cells positive for GranToxiLux (GTL), an indicator of granzyme B uptake, minus the percent of target cells positive for GTL when incubated with effector cells but without sera. For the Luciferase-based cytotoxicity assay, participant sera are incubated with IMC-infected cells and percent killing is measured through the use of ViviRen luminescence.

### **10.7.2 BnAb epitope binding and blocking assays**

Binding will be assessed using a panel of HIV-1 Env proteins to determine the number and proportion of each type (eg, clade) of Env proteins recognized by participant plasma samples at the primary immunogenicity timepoints and baseline. Blocking will be assessed by the ability of plasma antibody to block the binding of bnAbs to proteins known to bind those bnAbs.

### **10.7.3 Memory B cell sorts, clonal memory B cell cultures and recombinant antibody production**

Memory B cells may be sorted as individual cells for recovery of immunoglobulin genes, sequence analysis, and expression of recombinant mAbs. Genes recovered in this way will be analyzed by comparison to a reference gene set and for inference of the unmutated common ancestor of the antibody, determination of clonal lineage relationships among recovered genes, and compared with genes recovered from other vaccine studies and studies of HIV-1–infected persons. Recombinant mAbs may be assessed for binding, blocking, neutralization, ADCC, and other activities as described for plasma/serum assays.

Blood cell samples taken at timepoints appropriate for memory B cell sorting may also be placed into clonal memory B cell cultures. These cultures will be used to expand the memory B cell populations and supernatants from those cultures may be analyzed for binding, blocking, neutralization, and/or ADCC, or other assays as deemed appropriate. Clonally expanded cells can be immortalized to produce stable cell lines and/or subjected to gene recovery and mAb production.

### **10.7.4 Plasma cell sorts for B cell repertoire analysis**

Blood cell samples taken at timepoints appropriate for plasma cell sorting (~7 days after vaccination) may be sorted to isolate circulating plasmablasts/plasma cells. Cells isolated in this way may have gene isolation and analysis as described in Section [10.7.3](#).

### **10.7.5 Next generation sequencing (NGS) for VH and VL**

NGS will be performed by reverse transcription and PCR to amplify and sequence variable region gene segments from whole PBMC or isolated B cells from participants. Sequenced gene segments will be aligned to a reference database of variable regions of both heavy and light chain genes to determine gene usage and genetic features of each sequence. This may be performed using paired sequence techniques (eg, by droplet isolation) or on each chain individually.

### **10.7.6 RNAseq of Tfh and B cell populations**

Tfh and B cells will be isolated by flow cytometry either in bulk or as single cells and mRNA isolated. mRNA will be reverse transcribed and complementary DNA (cDNA) amplified for NGS. NGS reads will be aligned to the human reference genome and relative frequency of RNA transcripts in each population will be determined.

### **10.7.7 Genotyping**

Molecular human leukocyte antigen (HLA) typing may be performed on enrolled participants using cryopreserved PBMC collected at baseline, initially on specimens from participants who demonstrate vaccine-induced T-cell responses at

postvaccination timepoints. Other participants (including control recipients) may be HLA-typed to support future studies of immunological interest at the discretion of the HVTN Laboratory Program. Other genes, including those associated with immune responses (eg, immunoglobulin, or T cell receptor genes), or HIV-1 disease progression may also be assessed.

## **10.8 Specimen storage and other use of specimens**

The HVTN stores specimens from all study participants indefinitely, unless a participant requests that specimens be destroyed or if required by IRB/EC, or RE.

Other use of specimens is defined as studies not covered by the protocol or the ICF for the main study ([Appendix A](#)).

This research may relate to HIV, vaccines, the immune system, and other diseases. This could include genetic testing and, potentially, genome-wide studies. This research is done only to the extent authorized in each study site's ICF, or as otherwise authorized under applicable law. Other research on specimens ("other use") will occur only after review and approval by the HVTN, the IRB/EC of the researcher requesting the specimens, and the CRS's IRBs/ECs/REs if required.

As part of consenting for the study, participants document their initial decision to allow or not allow their specimens to be used in other research, and they may change their decision at any time. The participant's initial decision about other use of their specimens, and any later change to that decision, is recorded by their CRS in a Web-based tool that documents their current decisions for other use of their specimens. The HVTN will only allow other research to be done on specimens from participants who allow such use.

CRSs must notify HVTN Regulatory Affairs if institutional or local governmental requirements pose a conflict with or impose restrictions on specimen storage or other use of specimens.

## **10.9 Biohazard containment**

As the transmission of HIV and other blood-borne pathogens can occur through contact with contaminated needles, blood, and blood products, appropriate precautions will be employed by all personnel in the drawing of blood and shipping and handling of all specimens for this study, as currently recommended by the CDC and the NIH or other applicable agencies.

All dangerous goods materials, including Biological Substances, Category A or Category B, must be transported according to instructions detailed in the International Air Transport Association Dangerous Goods Regulations.

## **11 Safety monitoring and safety review**

### **11.1 Safety monitoring and oversight**

#### **11.1.1 HVTN 121 PSRT**

The HVTN 121 PSRT is composed of the following members:

- DAIDS medical officer representative
- Protocol chair and co-chair
- Protocol team leader
- Core medical monitor
- Protocol rheumatologist
- Clinical safety specialist

The clinician members of HVTN 121 PSRT are responsible for decisions related to participant safety.

The Protocol Team clinic coordinator, clinical data manager, vaccine developer representative, clinical trial manager, and others may also be included in HVTN 121 PSRT meetings.

#### **11.1.2 HVTN SMB**

The SMB is a multidisciplinary group consisting of biostatisticians, clinicians, and experts in HIV vaccine research that, collectively, has experience in the conduct and monitoring of vaccine trials. Members of the SMB are not directly affiliated with the protocols under review. An independent rheumatologist will also be available to the SMB to provide expert input on safety concerns related to SLE.

The SMB reviews safety data approximately every 4 months. The reviews consist of evaluation of cumulative reactogenicity events, AE, laboratory safety data, and individual reports of AEs requiring expedited reporting to DAIDS. The SMB conducts additional special reviews at the request of the HVTN 121 PSRT.

Study sites will receive SMB summary minutes and are responsible for forwarding them to their IRB/EC and any applicable RE.

### **11.1.3 SDMC roles and responsibilities in safety monitoring**

The roles and responsibilities of the SDMC in relation to safety monitoring include:

- Maintaining a central database management system for HVTN clinical data;
- Providing reports of clinical data to appropriate groups such as the HVTN 121 PSRT and HVTN SMB (see Section [11.1.2](#));

### **11.1.4 HVTN Core roles and responsibilities in safety monitoring**

- Daily monitoring of clinical data for events that meet the safety pause and HVTN 121 PSRT AE review criteria (see Section [11.3](#));
- Notifying HVTN CRSs and other groups when safety pauses or planned holds are instituted and lifted (see Section [11.3](#));
- Querying HVTN CRSs for additional information regarding reported clinical data; and
- Providing support to the HVTN 121 PSRT.

## **11.2 Safety reporting**

### **11.2.1 Submission of safety forms to SDMC**

Site staff must submit all safety forms (eg, reactogenicity, adverse experience, urinalysis, local lab results, and concomitant medications) before the end of the next business day, excluding federal or bank holidays. The forms should not be held in anticipation of additional information at a later date. If additional information is received at a later date, the forms should be updated and resubmitted before the end of the next business day after receiving the new information. For the case of a longer site holiday closure, site staff must submit the data by the end of the 5th day (local time) after receiving the information even if this day is a holiday.

For example: If the site becomes aware of an AE on Thursday (Day 0), the site must submit the data by the end of the next business day, on Friday. If there is a longer site holiday closure, then this AE must be reported no later than the end of the fifth day, Monday (Day 4). If Monday is a holiday as well, all safety forms still need to be submitted by the end of Monday (Day 4).

### **11.2.2 AE reporting**

An AE is any untoward medical occurrence in a clinical investigation participant administered a study product/procedure(s) and which does not necessarily have a

causal relationship with this treatment. An AE can therefore be any unfavorable and unintended sign (including an abnormal laboratory finding), symptom, or disease temporally associated with the use of an investigational study product/procedure(s), whether or not related to the investigational study product/procedure(s). All AEs are graded according to the DAIDS Table for Grading the Severity of Adult and Pediatric Adverse Events, Corrected Version 2.1, July 2017, available on the RSC website at <http://rsc.tech-res.com/clinical-research-sites/safety-reporting/daids-grading-tables>, except:

- Unintentional weight loss is required to be reported as an AE only if it is considered to be potentially deleterious to the participant’s health (see HVTN 121 *Study Specific Procedures*);
- Injection Site Erythema or Redness and Injection Site Induration or Swelling will not consider interference with usual social and functional activities such that:
  - Grade 1 is: 2.5 to < 5 cm in diameter OR 6.25 to < 25 cm^2 surface area;
  - Grade 2 is: ≥ 5 to < 10 cm in diameter OR ≥ 25 to < 100 cm^2 surface area;
  - Grade 3 is: ≥ 10 cm in diameter OR ≥ 100 cm^2 surface area OR Ulceration OR Secondary infection OR Phlebitis OR Sterile abscess OR Drainage;
  - Grade 4 is: Potentially life-threatening consequences (eg, abscess, exfoliative dermatitis, necrosis involving dermis or deeper tissue);
- Non-specific Rash or Skin Changes will be graded using the category of “Skin and subcutaneous tissue disorders – Other, specify” in the National Cancer Institute’s Common Terminology Criteria for Adverse Events (CTCAE), Version 5.0, November 2017, p.140 ([Table 11-1](#)):

**Table 11-1 Skin and subcutaneous tissue disorders**

Skin and subcutaneous disorders					
Grade					
Adverse Event	1	2	3	4	5
Skin and subcutaneous tissue disorders – Other, specify	Asymptomatic or mild symptoms; clinical or diagnostic observations only; intervention not indicated	Moderate; minimal, local or noninvasive intervention indicated; limiting age-appropriate instrumental activities of daily living (ADL)	Severe or medically significant, but not immediately life-threatening; hospitalization or prolongation of existing hospitalization indicated; disabling; limiting self-care ADL	Life-threatening consequences; urgent intervention indicated	Death

- Vasculitis will be graded using the category of “Vascular disorders” in the National Cancer Institute’s Common Terminology Criteria for Adverse Events (CTCAE), Version 5.0, November 2017, p.146 (Table 11-2):

**Table 11-2 Vascular disorders**

Vascular disorders					
Adverse Event	Grade				
	1	2	3	4	5
Vasculitis	Asymptomatic; intervention not indicated	Moderate symptoms; medical intervention indicated	Severe symptoms; medical intervention indicated (e.g., steroids)	Life-threatening; evidence of peripheral or visceral ischemia; urgent intervention indicated	Death
Definition: A disorder characterized by inflammation involving the wall of a vessel					

- Pericarditis will be graded using the category of “Cardiac disorders” in the National Cancer Institute’s Common Terminology Criteria for Adverse Events (CTCAE), Version 5.0, November 2017, p.8 (Table 11-3):

**Table 11-3 Cardiac disorders**

Cardiac disorders					
Adverse Event	Grade				
	1	2	3	4	5
Pericarditis	Asymptomatic; ECG or physical findings (e.g., rub) consistent with pericarditis	Symptomatic pericarditis (e.g., chest pain)	Pericarditis with physiologic consequences (e.g., pericardial constriction)	Life-threatening consequences; urgent intervention indicated	Death
Definition: A disorder characterized by irritation to the layers of the pericardium (the protective sac around the heart)					

- Myositis in SLE patients typically presents as muscle weakness, as opposed to pain; thus, myositis will be graded using the parameter of “Neuromuscular Weakness” in the DAIDS Table for Grading the Severity of Adult and Pediatric Adverse Events, Corrected Version 2.1, July 2017, p.16 (Table 11-4):

**Table 11-4 Neurologic adverse events**

Neurologic AEs				
Adverse Event	Grade			
	1	2	3	4
Neuromuscular Weakness (includes myopathy and neuropathy) Specify type, if applicable	Minimal muscle weakness causing no or minimal interference with usual social & functional activities OR No symptoms with decreased strength on examination	Muscle weakness causing greater than minimal interference with usual social & functional activities	Muscle weakness causing inability to perform usual social & functional activities	Disabling muscle weakness causing inability to perform basic self-care functions OR Respiratory muscle weakness impairing ventilation

- Leukopenia in an SLE flare is defined with the SELENA-SLEDAI instrument as a white blood cell count < 3,000 cells/mm^3. The cut point below which an individual is considered to have leukopenia (WBC, Decreased, > 7 days of age) as an AE according to the DAIDS Table for Grading the Severity of Adult and Pediatric Adverse Events, Corrected Version 2.1, July 2017 is 2,500 cells/mm^3. For the purposes of monitoring this parameter in this study, the cut point for a Grade 1 AE of WBC, Decreased (> 7 days of age) will be <3,000 cells/mm^3, such that study participants with a WBC in the range of 2,000 to 2,999 cells/mm^3 will be considered to have a Grade 1 AE of WBC, Decreased. The grading table applied for WBC, Decreased (> 7 days of age) will therefore be as follows (Table 11-5):

**Table 11-5 Lab parameters, hematology**

Lab Parameters, Hematology				
Adverse Event	Grade			
	1	2	3	4
WBC, Decreased (cells/mm  ; cells/L) > 7 days of age	2,000 to 2,999 2.000 x 10  to 2.999 x 10 	1,500 to 1,999 1.500 x 10  to 1.999 x 10 	1,000 to 1,499 1.000 x 10  to 1.499 x 10 	<1,000 <1.000 x 10 

- Lupus Pleurisy will be graded according to the following table. The components of Pleural Effusion and Pleuritic Pain have been extracted from the category of “Respiratory, thoracic and mediastinal disorders” in the National Cancer Institute’s Common Terminology Criteria for Adverse Events (CTCAE), Version 5.0, November 2017, p.129 (Table 11-6):

**Table 11-6 Respiratory, thoracic and mediastinal disorders**

Respiratory, thoracic and mediastinal disorders					
Adverse Event	Grade				
	1	2	3	4	5
Lupus Pleurisy Select the highest grade of the following components that are present: --Pleural Effusion* --Pleural Rub --Pleural Thickening --Pleuritic Pain*	Pleural Effusion: Asymptomatic; clinical or diagnostic observations only; intervention not indicated	Pleural Effusion: Symptomatic; intervention indicated (e.g., diuretics or limited therapeutic thoracentesis)	Pleural Effusion: Symptomatic with respiratory distress and hypoxia; surgical intervention including chest tube or pleurodesis indicated	Pleural Effusion: Life-threatening respiratory or hemodynamic compromise; intubation or urgent intervention indicated	Death
	Pleural Rub	–	–	–	–
	Pleural Thickening	–	–	–	–
	Pleuritic Pain: Mild pain	Pleuritic Pain: Moderate pain; limiting instrumental ADL	Pleuritic Pain: Severe pain; limiting self care ADL	–	–

- Pyuria in an SLE flare is defined with the SELENA/SLEDAI instrument as >5 WBC/high power field. Pyuria is not included in the DAIDS Table for Grading the Severity of Adult and Pediatric Adverse Events, Corrected Version 2.1, July 2017 or in the National Cancer Institute’s Common Terminology Criteria for Adverse Events (CTCAE) Version 5.0, November 2017; therefore, pyuria will be graded according to [Table 11-7](#):

**Table 11-7 Lab parameters, Urine testing**

Lab Parameters, Urine testing				
Adverse Event	Grade			
	1	2	3	4
Pyuria	6 to <10 WBCs per high power field	≥10 WBCs per high power field	Gross OR with WBC casts OR intervention indicated	Life-threatening consequences

All AEs are reported to the SDMC on the appropriate CRF. Clinic staff should evaluate every AE to determine if (1) the AE meets the requirements for expedited reporting to DAIDS (Section [11.2.3](#)) and (2) if the AE meets the criteria for a safety pause/prompt AE review (Section [11.3](#)).

Sites are expected to notify HVTN clinical safety staff of any serious safety concern requiring their attention ([Table 11-8](#)). Telephone numbers and email addresses are found on the protocol home page on the HVTN Members’ site (<https://members.hvtn.org/protocols/hvtn121>). Concerns requiring immediate attention should be communicated by calling the clinical safety phone.

In the case of email notification, clinical safety staff will reply during working hours (local time) to confirm that the email has been received and reviewed. If email service is not available, the CRS should notify clinical safety staff of the event by telephone, then submit CRFs.

In addition, site investigators are required to submit AE information in accordance with IRB/EC and any applicable RE requirements.

### 11.2.3 Expedited reporting of AEs to DAIDS

Requirements, definitions and methods for expedited reporting of AEs are outlined in Version 2.0 (January 2010) of the *Manual for Expedited Reporting of Adverse Events to DAIDS* (DAIDS EAE Manual), which is available on the RSC website at <http://rsc.tech-res.com/clinical-research-sites/safety-reporting/manual>. The SAE Reporting Category will be used for this study.

The internet-based DAIDS Adverse Experience Reporting System (DAERS) must be used for expedited AE (EAE) reporting to DAIDS. In the event of system outages or technical difficulties, EAE reports may be submitted via the DAIDS EAE Form. This form is available on the DAIDS RSC website at <http://rsc.tech-res.com/clinical-research-sites/safety-reporting/daids/paper-eae-reporting>.

For questions about DAERS, please contact [[contact]](mailto:[contact]) or from within the DAERS application itself.

For questions about EAE reporting, please contact the DAIDS RSC Safety Office at ([[contact]](mailto:[contact])).

The study product for which expedited reporting are required is:

- AIDS VAX® B/E

While the participant is in the study reporting period (see Section 3), the SAE Reporting Category will be used.

After the protocol-defined AE reporting period for the study, unless otherwise noted, only Suspected, Unexpected Serious Adverse Reactions as defined in Version 2.0 of the DAIDS EAE Manual must be reported to DAIDS, if the study staff become aware of the events.

The NIAID/DAIDS will report all unexpected SAEs related to the study products observed in this clinical trial to the FDA in accordance with 21 CFR 312.32 (IND Safety Reports).

For additional impact and management of SAEs on the study, see Section 11.3.

### **11.3 Safety pause and prompt PSRT AE review**

When a trial is placed on safety pause, all enrollment and vaccination with the product related to the event that triggered the pause will be held until further notice. The AEs that will lead to a safety pause or prompt HVTN 121 PSRT AE review are summarized in [Table 11-8](#). Vaccinations may be suspended for safety concerns other than those described in the table, or before pause rules are met, if, in the judgment of the HVTN 121 PSRT, participant safety may be threatened. Criteria for an individual participant's departure from the schedule of vaccinations are listed in Section [7.3](#).

**Table 11-8 AE notification and safety pause/AE review rules**

Event and relationship to study products	Severity	HVTN CRS action a	HVTN Core action
SAE, related	Grade 5 or Grade 4	Phone immediately, email and submit forms immediately	Immediate pause
SAE, not related	Grade 5	Phone immediately, email and submit forms immediately	Immediate PSRT notification
SAE, related	Grade 3, 2, or 1	Email and submit forms immediately	Immediate PSRT notification and prompt PSRT AE review to consider pause
AE b , related	Grade 4 or 3	Email and submit forms immediately	Immediate PSRT notification and prompt PSRT AE review to consider pause
“Severe” c SLE flare, regardless of relationship	N/A	Phone immediately, email and submit forms immediately	Prompt PSRT AE review
“Mild or moderate” d,e SLE flare, related	N/A	Phone immediately, email and submit forms immediately	Prompt PSRT AE review
3 or more confirmed “moderate” or “severe” SLE flares, regardless of relatedness	N/A	Phone immediately, email and submit forms immediately	Immediate pause

a Email addresses are found on the Protocol home page on the HVTN Members’ site (<https://members.hvtn.org/protocols/hvtn121>). Phone numbers for each pause rule are in the HVTN 121 SSPs.

b Does not include the following Grade 3 subjective reactogenicity symptoms: injection site pain, tenderness, fatigue/malaise, myalgia, arthralgia, chills, headache, nausea (unless IV rehydration required).

c “Severe” SLE flare is defined by application of the SELENA-SLEDAI instrument ([Appendix G](#)).

d “Moderate” SLE flare is defined by application of the SELENA-SLEDAI instrument ([Appendix G](#)), as well as the determination by a rheumatologist that the participant has flare components/symptoms/lab indices necessitating treatment with a dosage of Prednisone (or equivalent) in the range of >7.5 mg/day to < 0.5 mg/kg/day.

e “Mild” SLE flare is defined by application of the SELENA-SLEDAI instrument ([Appendix G](#)), as well as the determination by a rheumatologist that the participant has flare components/symptoms/lab indices necessitating treatment with a dosage of Prednisone (or equivalent) of ≤7.5 mg/day.

For all safety pauses, HVTN Core notifies the HVTN 121 PSRT, HVTN Regulatory Affairs, DAIDS Pharmaceutical Affairs Branch (PAB), DAIDS Regulatory Affairs Branch (RAB), DAIDS Safety and Pharmacovigilance Team (SPT), and participating HVTN CRSs. When an immediate safety pause is triggered, HVTN Core notifies the SMB.

Once a trial is paused, the HVTN 121 PSRT reviews safety data and decides whether the pause can be lifted or permanent discontinuation of vaccination is appropriate, consulting the SMB if necessary. HVTN Core notifies the participating HVTN CRSs, HVTN Regulatory Affairs, DAIDS PAB, DAIDS RAB, and DAIDS SPT of the decision regarding resumption or discontinuation of study vaccinations. Based on the HVTN 121 PSRT assessment, DAIDS RAB notifies the FDA as needed.

If an immediate HVTN 121 PSRT notification or prompt HVTN 121 PSRT AE review is triggered, HVTN Core notifies the HVTN 121 PSRT as soon as possible

during working hours (local time)—or, if the information was received during off hours, by the morning of the next work day. If a prompt HVTN 121 PSRT AE review cannot be completed within 72 hours of notification (excluding weekends and US federal holidays), an automatic safety pause occurs.

The HVTN requires that each CRS submit to its IRB/EC and any applicable RE protocol-related safety information (such as IND safety reports, notification of vaccine holds due to the pause rules, unanticipated problems involving risks to participants or others, and notification of other unplanned safety pauses). CRSs must also follow all applicable RE reporting requirements.

In addition, all other AEs are reviewed routinely by the HVTN 121 PSRT (see Section [11.4.2](#)).

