4		Urinary casts	Heme-granular or red blood cell casts.
4		Hematuria	>5 red blood cells/high power field. Exclude stone, infection or other cause.
4		Proteinuria	New onset or recent increase of more than 0.5 gm/24 hours.
4		Pyuria	>5 white blood cells/high power field. Exclude infection.
2		Rash	Ongoing inflammatory lupus rash.
2		Alopecia	Ongoing abnormal, patchy or diffuse loss of hair due to active lupus.
2		Mucosal ulcers	Ongoing oral or nasal ulcerations due to active lupus.
2		Pleurisy	Classic and severe pleuritic chest pain or pleural rub or effusion or new pleural thickening due to lupus.
2		Pericarditis	Classic and severe pericardial pain or rub or effusion, or electrocardiogram confirmation.
2		Low complement	Decrease in CH50, C3 or C4 below the lower limit of normal for testing laboratory.
2		Increased DNA binding	>25% binding by Farr assay or above normal range for testing laboratory.
1		Fever	>38°C. Exclude infectious cause.
1		Thrombocytopenia	<100,000 platelets/mm  .
1		Leukopenia	<3,000 white blood cells/mm  . Exclude drug causes.

_____ TOTAL SCORE (Sum of weights next to descriptors marked present)
			

Categorize as "Mild or Moderate" Flare or "Severe" Flare if the patient has at least one of the listed criteria in that category:	
Mild or Moderate Flare 	Severe Flare 
 Increase in SLEDAI $\geq$ 3 points, but not > 12	 Increase to a SLEDAI > 12

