 New/worse: 
 
• Discoid, photosensitive, profundus, cutaneous vasculitis, bullous lupus
 
• Nasopharyngeal ulcers
 
• Pleuritis
 
• Pericarditis
 
• Arthritis
 
• Fever (SLE)
 
	 New/worse: 
 
• CNS-SLE
 
• Vasculitis
 
• Nephritis
 
• Myositis
 
• Platelet count < 60,000 (equivalent to <math>60 \times 10^9/L</math>)
 
• Hemolytic anemia: Hemoglobin <7.0 g/dL or decrease in Hemoglobin >3.0 g/dL
 
 Requiring a doubling of prednisone dose, or prednisone increase to >0.5 mg/kg/day, and/or hospitalization
 Increase in prednisone, but not to >0.5 mg/kg/day	 Increase in prednisone to >0.5 mg/kg/day
 Added NSAID or Plaquenil (hydroxychloroquine) for SLE activity	 New Cytoxan (cyclophosphamide), Azathioprine, Methotrexate for SLE activity
 Hospitalization for SLE activity	
 $\geq$ 1.0 Increase in Physician's Global Assessment (PGA) score, but not to more than 2.5	 Increase in Physician's Global Assessment (PGA) score to > 2.5

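### Table 11-8 footnote d stops moderate flares just short of 0.5 mg/kg/day while Appendix G starts severe just above it, so a flare needing exactly that dose is not counted toward the three-flare pause

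*Combined protocol and SAP*

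**What the plan says.** The last row of Table 11-8 (Section 11.3) requires an immediate pause after three or more confirmed moderate or severe "SLE flares, regardless of relatedness". Appendix G has no separate moderate class. It has one joint mild-or-moderate column and one severe column, and a flare goes into a column "if the patient has at least one of the listed criteria in that category". The footnotes to Table 11-8 supply the split:

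- Footnote c: severe is whatever Appendix G calls severe, with no dose rule of its own.
- Footnote d: moderate is an Appendix G flare that a rheumatologist also judges to be "necessitating treatment with a dosage of Prednisone (or equivalent) in the range of >7.5 mg/day to < 0.5 mg/kg/day".
- Footnote e: mild is the same with the dose condition "necessitating treatment with a dosage of Prednisone (or equivalent) of ≤7.5 mg/day".

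The prednisone criterion in Appendix G's joint column is "Increase in prednisone, but not to >0.5 mg/kg/day". In the severe column it is "Increase in prednisone to >0.5 mg/kg/day".

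**The concern.** Footnote d and Appendix G treat the same boundary differently. The joint column includes 0.5 mg/kg/day and the severe column begins above it, but footnote d ends below it. A flare at the boundary therefore belongs to Appendix G's joint category yet meets neither label that the pause rule counts.

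This matters because the pause rule is a fixed trigger in a single-arm trial with no concurrent control. An immediate pause also brings automatic notification of the Safety Monitoring Board, whose routine reviews are about four months apart (Sections 11.1.2 and 11.3). For an unrelated, non-fatal flare that is not severe, the three-flare count is the only row of Table 11-8 that could apply. A rising severity scale that counts the doses on either side of a point but not the point itself has no evident rationale.

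**Working it through.** **Is a count of three within reach?** This is context only. Section 6.1.1.2 plans on 3.9% of patients flaring per month and states 6.1 incidents per year. The figure reproduces: 16 × (1 − 0.961^12) = 16 × 0.3796 = 6.07. That section defines a flare as a rise of 4 or more in SLEDAI, which is not the Appendix G composite, and it does not split flares by dose. It shows that three flares are plausible, but it says nothing about how many would be moderate or severe.

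**Can the boundary dose be mild?** Inclusion criterion 2 (Section 7.1) requires weight above 110 pounds. 110 × 0.45359 = 49.895 kg, and 49.895 × 0.5 = 24.95 mg/day. At entry weight, 0.5 mg/kg/day is therefore always well above the 7.5 mg/day limit of footnote e, so the boundary dose is never mild.

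**Classification by the literal inequalities.** Take a 60 kg participant on no prednisone who develops new arthritis (weight 4) and pleurisy (weight 2). SLEDAI rises from 0 to 6. That is at least 3 and not above 12, and neither manifestation is on Appendix G's severe list.

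| Prednisone needed | mg/kg/day | Footnote d (>7.5 mg/day and <0.5 mg/kg/day) | Severe by dose (>0.5) | Counted toward pause |
|---|---|---|---|---|
| 25 mg/day | 25/60 = 0.417 | yes | no | yes |
| 30 mg/day | 30/60 = 0.500 | no | no | **no** |
| 35 mg/day | 35/60 = 0.583 | no | yes | yes |

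The same check at 50, 60, 70, 80, 90 and 100 kg gives the same pattern: exactly 0.5 mg/kg/day falls in no class, 2.5 mg/day less is moderate, and 2.5 mg/day more is severe.

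**Effect on the rule.** With three flares that would otherwise count and one at the boundary, the count is 3 − 1 = 2, below the trigger. The automatic pause would need a further countable flare.

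**After changing < to ≤ in footnote d.** The 0.500 row becomes moderate and counts. No other dose moves, and there is no overlap with severe, which begins strictly above 0.5.

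**The case against.** **The case is narrow.** With tablets in 2.5 mg steps (an assumption; the documents do not give one), a fixed dose equals 0.5 mg/kg exactly only at weights that are multiples of 5 kg. That is 1 in 50 weights recorded to 0.1 kg (5/0.1 = 50). At 61 kg, 30 mg/day is 30/61 = 0.492 mg/kg/day, which is moderate. At 67 kg the boundary dose is 33.5 mg/day. This stands, and the 60 kg example should not suggest that the case is common. The likelier route is an order written as 0.5 mg/kg/day, which lands on the boundary at any weight.

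**A rheumatologist would not leave such a flare unclassified.** Footnote d does involve a rheumatologist's determination, but that determination is whether the treatment needed falls inside the stated range, and the range excludes the boundary. Sensible practice may repair the text, but it does not make the text right.

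**Other safeguards exist.** The safety review team includes a rheumatologist, may suspend vaccination before pause rules are met, and reviews safety reports weekly during the injection phase (Sections 11.1.1, 11.3 and 11.4.2). Daily review separately covers events needing expedited reporting, which brings in serious flares (Sections 11.2.3 and 11.4.1). Related Grade 3 or 4 events and related Grade 1 to 3 serious events already lead to "Immediate PSRT notification and prompt PSRT AE review to consider pause". These limit the harm, but none of them is the pre-specified count.

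**A reader might also fault footnote e** for not placing flares that need no prednisone, since Appendix G admits them through criteria such as "Added NSAID or Plaquenil (hydroxychloroquine) for SLE activity". The documents do not support treating that as an error. A limit of ≤7.5 mg/day already admits zero, such a flare is not moderate on either reading, and the pause count does not change. Section 4.3 promises additional review of flares, which routine review can satisfy.

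**Conclusion.** Wrong as written, minor. Footnote d's upper bound does not meet Appendix G's lower bound for severe. A flare needing exactly 0.5 mg/kg/day, with no other Appendix G severe criterion, drops out of the automatic three-flare pause.

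This rests on reading the inequalities literally. It also assumes that the Study Specific Procedures and the flare form, which are not in the documents, do not already correct the bound. A boundary flare that meets any other severe criterion is still counted.

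Three stronger conclusions might be inferred and are not supported:

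- **A stated loss in the chance of pausing.** The documents give neither the share of flares that are moderate or severe nor the share at this dose, so no probability is claimed.
- **A pause that cannot happen until a fourth flare.** Only the automatic trigger waits; the safety review team can act sooner.
- **Loss of prompt review for related flares at this dose.** That row carries Appendix G's joint label, so the loss depends on reading the footnotes as narrowing it, and the more serious related events have rows of their own.

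**What to change.** In Table 11-8 footnote d, change the upper bound to ≤ 0.5 mg/kg/day and state that any Appendix G severe criterion takes precedence. Make the same change in the flare form or the Study Specific Procedures if they repeat the range. Footnote e can stay as it is.

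The cost is one changed inequality and one clause, by clarification memo or letter of amendment, both of which Section 13 provides for. No visits, tests or data items are added. The downside is that the pause may trigger slightly more often.

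The change closes this gap only. It does not guarantee that every flare falls in exactly one class. Exclusion criterion 12 allows baseline prednisone up to 10 mg/day, and the footnotes do not say whether the total or the added dose is meant. New mycophenolate is not on Appendix G's severe drug list, although Section 7.3.3 makes it a reason to stop an individual's vaccination.
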